5.0 TREATMENT PLAN

5.1 Product Information

5.1.1 Drug Ordering and Accountability

Bristol-Meyers Squibb is supplying study drug. Please see Appendix H for information on provisions for ordering study drug from BMS. It is possible that sites may have more than one clinical study on the same drug ongoing at the same time. It is imperative that only drug product designated for this protocol be used for this study. The investigator is responsible for ensuring that the investigational product is stored under the appropriate environmental conditions (temperature, light, and humidity). If concerns regarding the quality or appearance of the investigational product arise, do not dispense the investigational product, and contact BMS immediately.

It is the investigator's responsibility to ensure that arrangements have been made for drug destruction, including the disposal, and that procedure for proper disposal have been established according to applicable regulations, guidelines, and institutional procedures.

5.1.2 Product Description and Dosage Form

Please provide information on the product as shown in the sample table below:

Product Description & Dosage Form	Potency	Primary Packaging (Volume)/ Label Type	Secondary Packaging (Qty)/ Label Type	Appearance	Storage Conditions (per label)
Nivolumab BMS-936558- 01 Solution for	100 mg (10 mg/mL)	10 mL vial	5 or 10 vials per carton/ Open-label	Clear to opalescent colorless to	2 to 8°C. Protect from light and
Injectiona	111g/111L)			pale yellow	freezing

				liquid. May contain particles		
Ipilimumab Solution for Injection	200 mg (5 mg/mL)	40 mL vial	4 vials per carton/Open-label	Clear, colorless to pale yellow liquid. May contain particles	2 to Protect light freezing.	8°C. from and

^aNivolumab may be labeled as BMS-936558-01 or Nivolumab Solution for Injection

If stored in a glass front refrigerator, vials should be stored in the carton. Recommended safety measures for preparation and handling of nivolumab and ipilimumab include laboratory coats and gloves. For additional details on prepared drug storage and use time of nivolumab or ipilimumab under room temperature/light and refrigeration, please refer to the BMS-936558 (nivolumab) and Ipilimuab Investigator Brochure section for "Recommended Storage and Use Conditions."

5.2 Treatment Schema

- Patients must sign informed consent and be registered.
- Informed consent should be signed within 60 days prior to beginning of ASCT conditioning. Subject recruitment and informed consent will take place in the BMT Service at HackensackUMC and in the BMT service at Georgetown University. Patients who already had stem cell mobilization and collection will also be allowed to sign informed consent and be enrolled in the trial.
- The first administration of study therapy will be administered in the BMT Service.
- 14 to 21 days after stem cell infusion, if ANC>800 (off growth factors for at least 3 days) and Platelets>20,000 without transfusion, ipilimumab and nivolumab should be started.
- Delay initiation of post ASCT therapy until ANC>800 (off growth factors for at least 3 days) and Platelets>20,000 without transfusion up to 28 days after stem cell infusion.
- Post ASCT therapy may be delayed up to 28 days after stem cell infusion if deemed appropriate by the investigator.
- The first day of ipilimumab/nivolumab infusion will be considered Day 1 of Week 1. Prior to patient's drug administration on Day 1 of Week 1, all patients must be re-assessed to confirm eligibility.
- Laboratory assessments must be evaluated within 72 hours prior to re-dosing
- All visits will be given a +/- 2-day window.
- At screening visit and each subsequent visit, the patient should be given a stool collection kit.

Group A	De novo diffuse large B cell lymphoma that fails to achieve a PET negative complete response to primary rituximab and anthracycline based multi-
	agent chemotherapy and at least maintains stable disease after salvage
	chemotherapy or present double/triple hit features defined by
	overexpression by standard immunohistochemistry of c-MYC plus BCL2
	and/or BCL6 or presence of chromosomal translocations as detected by
	break-apart FISH involving IGH/MYC plus IGH/BCL2 and/or IGH/BCL6 and
	who only received standard chemoimmunotherapy with rituximab,
	cyclophosphamide, vincristine and prednisone (R-CHOP) for induction and
	present at least stable disease after consolidation or salvage
	chemotherapy.

Group B	Recurrent high-risk diffuse large B cell lymphoma defined as relapsing within one year of completion of rituximab and anthracycline based multiagent chemotherapy or a sAAIPI (second-line age-adjusted International Prognostic Index) intermediate or high at relapse or acquisition of double/triple hit features upon relapse (as defined in group A) and at least stable disease after salvage chemotherapy. Patients with an initial diagnosis of low-grade/indolent non-Hodgkin lymphoma (i.e. follicular, marginal zone) who present relapse with histologic transformation to diffuse large B cell lymphoma (confirmed by biopsy) and meet the definition for high-risk as presented above, are also eligible.
Group C	De novo high-risk T cell lymphoma with at least stable disease after primary therapy. Patients with ALK-positive ALCL will be excluded from the trial. Patients with ALK-negative ALCL in complete response will be excluded from the trial.
Group D	Recurrent T cell lymphoma with at least stable disease after salvage therapy. Patients with ALK-positive ALCL will be excluded from the trial.

5.3 Administration

Nivolumab 3 mg/kg for 12 doses, on day 1 of weeks 1, 4, 7, 10, 12, 14, 16, 18, 20, 22, 24, 26 lpilimumab 1 mg/kg for 6 doses, on day 1 of weeks 1, 4, 7, 10, 16, 22

Nivolumab is to be administered as a 60-minute IV infusion, using a volumetric pump with a 0.2/1.2 micron pore size, low-protein binding polyethersulfone membrane in-line filter at the protocol-specified dose. The drug can be diluted with 0.9% normal saline for delivery but the total drug concentration of the solution cannot be below 1 mg/mL. It is not to be administered as an IV push or bolus injection. At the end of the infusion, flush the line with a sufficient quantity of normal saline.

Ipilimumab is to be administered as a 90-minute IV infusion, using a volumetric pump with a 0.2/1.2 micron low-protein binding in-line filter. Ipilimumab is given undiluted or further diluted in 0.9% NaCl Injection, USP or 5% Dextrose Injection, USP in concentrations between 1 mg/mL and 4 mg/mL.

The dosing calculations should be based on the actual screening body weight. If the subject's weight on the day of dosing differs by > 10% from the weight used to calculate the dose, the dose must be recalculated. All doses should be rounded up or to the nearest milligram per institutional standard. There will be no dose modifications allowed.

When infusions of ipilimumab and nivolumab are given on the same day, the preferred treatment is to give nivolumab followed by ipilimumab. Separate infusion bags and filters must be used for each infusion. The nivolumab infusion must be promptly followed by a saline flush to clear the line of nivolumab before starting the ipilimumab infusion. The second infusion will always be ipilimumab, and will start approximately 30 minutes after completion of the nivolumab infusion.

Patients may be dosed 2 days prior or up to 2 days after the scheduled date, if necessary. The original scheduled date should be adhered to throughout the protocol.

Toxicity management for the combined agents follows the same template guidelines and algorithms for single agent nivolumab.

5.4 Dose Modifications

There will be no dose modifications permitted for study drug, with the exception of changes due to fluctuation in weight. Dose reductions or dose escalations are not permitted.

5.5 Premedication

Only needs to be given for transfusion reactions (See Appendix G for Transfusion Reactions)

5.6 Management Algorithms for Immuno-Oncology Agents

Immuno-oncology (I-O) agents are associated with adverse events that can differ in severity and duration than adverse events caused by other therapeutic classes. Nivolumab and ipilimumab are considered immuno-oncology agents in this protocol. Management algorithms have been developed to assist investigators in assessing and managing the following groups of adverse events: Gastrointestinal, Renal, Pulmonary, Hepatic, Endocrinopathies, Skin, and Neurological.

Early recognition and intervention are recommended according to the management algorithms; and in addition include ophthalmologic evaluations for any visual symptoms in order to evaluate for nivolumab or ipilimumab related uveitis.

The recommendations are to follow the algorithms in the nivolumab investigator brochure for immune related events; while the ipilimumab investigator brochure contains similar algorithms, the algorithms in the nivolumab brochure have been aligned to accommodate combinations as well as nivolumab monotherapy. Therefore, the algorithms recommended for utilization are in Appendix G for reference.

For subjects expected who require more than 4 weeks of corticosteroids or other immunosuppressants to manage an adverse event, consider the following recommendations

- Antimicrobial/antifungal prophylaxis per institutional guidelines to prevent opportunistic infections such as Pneumocystis jiroveci and fungal infections.
- Early consultation with an infectious disease specialist should be considered. Depending on the presentation, consultation with a pulmonologist for bronchoscopy or a gastroenterologist for endoscopy may also be appropriate.
- In patients who develop recurrent adverse events in the setting of ongoing or prior immunosuppressant use, an opportunistic infection should be considered in the differential diagnosis.

Additional details on the safety of nivolumab and ipilimumab, including results from clinical studies, are available in the IB.

5.7 Dose Delay Criteria

Dose delay criteria apply for all drug-related adverse events (regardless of whether or not the event is attributed to nivolumab, ipilimumab or both). All study drugs must be delayed until treatment can resume. In the case that a treatment cannot be administered at a scheduled visit (with +/-2 day window), proceed to the next scheduled dose.

Nivolumab and ipilimumab administration should be delayed for the following:

• Any Grade ≥ 2 non-skin, drug-related adverse event, with the following exceptions:

- Grade 2 drug-related fatigue or laboratory abnormalities do not require a treatment delay
- Any Grade 3 skin, drug-related adverse event
- Any Grade 3 drug-related laboratory abnormality, with the following exceptions for asymptomatic amylase or lipase, AST, ALT, or total bilirubin:
 - Grade 3 amylase or lipase abnormalities that are not associated with symptoms or clinical manifestations of pancreatitis do not require a dose delay. It is recommended to consult with the principle investigator for Grade 3 amylase or lipase abnormalities.
 - If a subject has a baseline AST, ALT, or total bilirubin that is within normal limits, delay dosing for drug-related Grade ≥ 2 toxicity
 - If a subject has baseline AST, ALT, or total bilirubin within the Grade 1 toxicity range, delay dosing for drug-related Grade ≥ 3 toxicity
- Any adverse event, laboratory abnormality, or intercurrent illness which, in the judgment of the investigator, warrants delaying the dose of study medication.

5.8 Criteria to Resume Treatment

Subjects may resume treatment with study drug when the drug-related AE(s) resolve to Grade ≤1 or baseline value, with the following exceptions:

- Subjects may resume treatment in the presence of Grade 2 fatigue
- Subjects who have not experienced a Grade 3 drug-related skin AE may resume treatment in the presence of Grade 2 skin toxicity
- Subjects with baseline Grade 1 AST/ALT or total bilirubin who require dose delays for reasons other than a 2-grade shift in AST/ALT or total bilirubin may resume treatment in the presence of Grade 2 AST/ALT OR total bilirubin
- Subjects with combined Grade 2 AST/ALT AND total bilirubin values meeting discontinuation parameters (Section 5.9) should have treatment permanently discontinued
- Drug-related pulmonary toxicity, diarrhea, or colitis, must have resolved to baseline before treatment is resumed
- Drug-related endocrinopathies adequately controlled with only physiologic hormone replacement may resume treatment

If the criteria to resume treatment are met, the subject should restart treatment at the next scheduled timepoint per protocol. However, if the treatment is delayed past the next scheduled timepoint per protocol, the next scheduled timepoint will be delayed until dosing resumes.

If treatment is delayed > 6 weeks, the subject must be permanently discontinued from study therapy, except as specified in discontinuation Section 5.9.

Peripheral blood and stool sample collection will continue to take place for subjects discontinued from the study up to 18 months post ASCT and/or relapse, if it occurs.

5.9 Discontinuation Criteria

Treatment should be permanently discontinued for the following:

 Any Grade 2 drug-related uveitis or eye pain or blurred vision that does not respond to topical therapy and does not improve to Grade 1 severity within the re-treatment period OR requires systemic treatment

Amendment9 09NOV2021 Page 30 of 77

- Any Grade 3 non-skin, drug-related adverse event lasting > 7 days, with the following exceptions for drug-related laboratory abnormalities, uveitis, pneumonitis, bronchospasm, diarrhea, colitis, neurologic adverse event, hypersensitivity reactions, and infusion reactions
 - Grade 3 drug-related uveitis, pneumonitis, bronchospasm, diarrhea, colitis, neurologic adverse event, hypersensitivity reaction, or infusion reaction of any duration requires discontinuation
 - Grade 3 drug-related laboratory abnormalities do not require treatment discontinuation except those noted below
 - Grade 3 drug-related thrombocytopenia > 7 days or associated with bleeding requires discontinuation
 - Any drug-related liver function test (LFT) abnormality that meets the following criteria require discontinuation:
 - AST or ALT > 8 x ULN
 - Total bilirubin > 5 x ULN
 - Concurrent AST or ALT > 3 x ULN and total bilirubin > 2 x ULN
- Any Grade 4 drug-related adverse event or non-hematological laboratory abnormality, except for the following events which do not require discontinuation:
 - o Isolated Grade 4 amylase or lipase abnormalities that are not associated with symptoms or clinical manifestations of pancreatitis and decrease to < Grade 4 within 1 week of onset.
 - Isolated Grade 4 electrolyte imbalances/abnormalities that are not associated with clinical sequelae and are corrected with supplementation/appropriate management within 72 hours of their onset
- Any dosing interruption lasting > 6 weeks with the following exceptions:
 - Dosing interruptions to allow for prolonged steroid tapers to manage drug-related adverse events are allowed. Prior to re-initiating treatment in a subject with a dosing interruption lasting > 6 weeks, the Investigator must be consulted. Tumor assessments should continue as per protocol even if dosing is interrupted
 - Dosing interruptions > 6 weeks that occur for non-drug-related reasons may be allowed if approved by the Investigator. Prior to re-initiating treatment in a subject with a dosing interruption lasting > 6 weeks, the Investigator must be consulted. Tumor assessments should continue as per protocol even if dosing is interrupted
- Any adverse event, laboratory abnormality, or intercurrent illness which, in the judgment
 of the Investigator, presents a substantial clinical risk to the subject with continued
 nivolumab or ipilimumab dosing
- Any patient that meets disease-specific criteria for relapse or progressive disease should be discontinued from study therapy.

Peripheral blood and stool sample collection will continue to take place for subjects discontinued from the study up to 18 months post ASCT and/or at relapse, if it occurs.

6.0 SUBJECT SCREENING EVALUATION

- 6.1 Evaluation of the patient after informed consent is signed. Any of the evaluations listed below will be accepted if performed prior to signing consent if done within the described timeframe, without need for repeating procedures.
- History and physical examination within 30 days prior to start of ASCT conditioning regimen.

Amendment9 09NOV2021 Page 31 of 77

- CBC, differential, haptoglobin, LFTs, total CK, complete metabolic panel within 30 days prior to start of ASCT conditioning regimen.
- Evaluation for CMV, HIV, HTLV, and hepatitis B & C within 30 days prior to start of ASCT conditioning regimen.
- Baseline electrocardiogram (EKG) and MUGA scan or echocardiogram with measurement of LVEF within 90 days prior to start of ASCT conditioning regimen.
- Chest radiography within 90 days prior to start of ASCT conditioning regimen.
- Pulmonary function test (PFT) within 90 days prior to start of ASCT conditioning regimen.
- Cut-off values for the above-mentioned studies will be consistent with institutional standard operating procedures (SOPs) for eligibility screening prior to ASCT.
- For groups A,B,C,D: PET-CT scan **and** CT scan with intravenous/oral contrast of neck, chest, abdomen and pelvis within 30 days prior to initiation of ASCT conditioning
- For groups E and F: Within 30 days prior to initiation of ASCT conditioning: Serum protein electrophoresis with immunofixation, quantitative serum IgG, IgM, IgA (IgE in cases where this is the involved immunoglobulin), serum free light chains, 24-hour urine for protein electrophoresis with immunofixation and protein quantification.
- For groups E and F: Within 30 days prior to initiation of ASCT conditioning: Skeletal Survey.
- For all groups, within 30 days prior to ASCT conditioning (at the time of informed consent): Peripheral blood collection for blood immune phenotype and metabolomics analysis.
- For all groups post consent, prior to ASCT conditioning: Stool samples will be collected for baseline gut microbiome analysis.
- For all groups: Acquisition of tumor tissue biopsy (either new or archival tissue, if available) or bone marrow biopsy (if known involvement) for evaluation of PD1/PDL1 expression and baseline tumor immune profile. Tumor Biopsies and/or Bone Marrow Biopsies for Lymphoma subjects (Groups A through D) and Bone Marrow Biopsies for Multiple Myeloma subjects (Groups E & F) will be collected at screening, end of treatment, complete response, and at relapse, if clinically indicated. For Bone Marrow Biopsies, the research sample will be collected (aspirate, send the first pull, yellow top tube) to [name] lab. Additional samples for all disease groups will be sent to pathology for immunostaining of fixed tissue for PDL1 expression on tumor cells and for the in situ presence of CD4 and CD8 T cells with PD1 expression. If viable biopsy material is unavailable for research purposes, [name] lab will access fixed archival tumor materials for preparing tumor lysates and possibly for retrieving T cell DNA for repertoire analysis. Samples for Georgetown University subjects are to be shipped via Fed Ex on the day of collection tubes banded in sealed plastic bag and wrapped in bubble wrap at room temperature to [name] lab.

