4.0 PATIENT ELIGIBILITY

4.1 Inclusion Criteria

In order to be eligible for participation in this trial, the subject must meet the following inclusion criteria:

- 1. Voluntary signed and dated IRB/IEC approved written informed consent form in accordance with regulatory and local guidelines.
- 2. Be 18 years or older and 80 years or younger on the day of signing consent
- 3. Have a confirmed diagnosis of:
 - o (GROUP A) De novo diffuse large B cell lymphoma that fails to achieve a PET negative complete response to primary rituximab and anthracycline based multiagent chemotherapy and at least maintains stable disease after salvage chemotherapy or present double/triple hit features defined by overexpression by standard immunohistochemistry of c-MYC plus BCL2 and/or BCL6 or presence of chromosomal translocations as detected by break-apart FISH involving IGH/MYC plus IGH/BCL2 and/or IGH/BCL6 and who only received standard chemoimmunotherapy with rituximab, cyclophosphamide, vincristine and prednisone (R-CHOP) for induction and present at least stable disease after consolidation or salvage chemotherapy. Stable disease (SD) for lymphoma is defined in Appendix B: Lugano Classification for Response Assessment of Non-Hodgkin Lymphoma.
 - O (GROUP B) Recurrent high-risk diffuse large B cell lymphoma defined as relapsing within one year of completion of rituximab and anthracycline based multi-agent chemotherapy or a sAAIPI (second-line age-adjusted International Prognostic Index) intermediate or high at relapse or acquisition of double/triple hit features upon relapse (as defined in group A) and at least stable disease after salvage chemotherapy. Patients with an initial diagnosis of low-grade/indolent non-Hodgkin lymphoma (i.e. follicular, marginal zone) who present relapse with histologic transformation to diffuse large B cell lymphoma (confirmed by biopsy) and meet the definition for high-risk as presented above, are also eligible.
 - O (GROUP C) De novo high-risk T cell lymphoma with at least stable disease after primary therapy. High risk T cell lymphoma is defined as Stage III or IV disease at presentation and/or failure to achieve CR after frontline chemotherapy. Patients with ALK-positive ALCL will be excluded from the trial. Patients with ALK-negative ALCL in complete response will be excluded from the trial.

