6.2 Evaluation and Response

6.2.1 For Groups A, B, C, and D:

- PET-CT scan and/or CT scan with intravenous/oral contrast of neck, chest, abdomen and pelvis will be performed for response evaluation 90-100 days post ASCT, 180-200days post ASCT, 360-380 days post ASCT and 540-560 days post ASCT. Response criteria will follow the Lugano Classification (see Appendix B). Both PET/CT and CT scan should be done within 30 days prior to initiation of ASCT conditioning for baseline response evaluation purposes. Either PET/CT or CT scan are acceptable for response evaluation after ASCT, and should be compared to the pre-ASCT baseline scan.
- Physical exam, laboratory work-up and correlative studies will be performed as delineated in the Clinical Trial Flowchart (Appendix D)

Amendment9 09NOV2021 Page 32 of 77

6.2.2 For Groups E and F:

- Serum protein electrophoresis with immunofixation, quantitative serum IgG, IgM, IgA (IgE or IgD in cases where this is the involved immunoglobulin), serum free light chains, 24-hour urine for protein electrophoresis with immunofixation and protein quantification will be collected for response evaluation 30-40 days post ASCT, 60-70 days post ASCT, 90-100 days post ASCT, 180-200 days post ASCT, 270-290 days post ASCT, 360-380 days post ASCT, 450-470 days post ASCT and 540-560 days post ASCT. Response criteria will follow the International Myeloma Working Group (IMWG) Uniform Response Criteria for Multiple Myeloma (see Appendix C). For patients who achieve CR by IMWG Criteria, a bone marrow biopsy will be required for confirmation and tumor immunophenotype analysis
- Physical exam, laboratory work-up, and correlative studies will be performed as delineated in the Clinical Trial Flowchart (Appendix D)

6.2.3 For All Groups:

- If a patient signs consent but does not receive treatment, the patient will not be evaluable and no further safety information will be collected. The slot will be released and may be re-assigned to another patient.
- If there is progressive disease or relapse documented by any of the criteria, a confirmatory lymph node and/or bone marrow biopsy will be performed for confirmation of disease relapse and tumor immunophenotype studies.

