8.4.2 Evaluation of tumor site phenotype

Absolute number of PD-L1/L2-bearing activated helper T cell subpopulations from biopsy at tumor site will be examined for two time points prior to conditioning and time of progression (within 18 months post-transplant) using Poisson regression analysis with GEE described in analysis of blood phenotype above.

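### The tumour-site before/after comparison permits unlike specimens at its two time points and cannot separate specimen source from real change

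*Combined protocol and SAP*

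**What the plan says.** **Baseline specimen.** The tissue item in section 6.1 asks for "Acquisition of tumor tissue biopsy (either new or archival tissue, if available) or bone marrow biopsy (if known involvement"), to serve PD-1/PD-L1 evaluation and the baseline immune profile of the tumour. Most other screening items in 6.1 carry a 30- or 90-day window; this one has none. For marrow, "the research sample will be collected (aspirate, send the first pull, yellow top tube"). If no viable material exists, the laboratory "will access fixed archival tumor materials for preparing tumor lysates" and possibly to recover T cell DNA.

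**Progression specimen.** Section 6.2.3 says that on documented progression or relapse "a confirmatory lymph node and/or bone marrow biopsy will be performed for confirmation of disease relapse and tumor immunophenotype studies". The tissue item in 6.1 and footnote k of Appendix D instead make tumour and marrow collection, relapse included, depend on clinical indication.

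**Analysis.** Section 8.4.2 takes the absolute number of PD-L1/L2-bearing activated helper T cells in the tumour-site biopsy, which "will be examined for two time points prior to conditioning and time of progression", by the Poisson GEE method used for blood. Section 8.3.4 specifies that method with a log link and independent covariance. Infection status is the only adjustment covariate named there for the immune-marker models.

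**The concern.** The comparison is meant to show how the tumour's immune environment differs between the period before conditioning and progression. The collection rules allow one patient to supply an older node block at baseline and a marrow sample at progression, and another to supply a new node biopsy at both. The outcome is a raw number of cells, so it depends on how much tissue was taken and from where. An aspirate and a solid biopsy do not yield counts on one scale.

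Nothing in 8.4.2 matches specimens within a patient, adjusts for their source or normalises for amount. Restricting the analysis to patients with both samples would not solve this, because a complete pair can still be mismatched. The risk is a reported rise or fall that reflects which specimens happened to be available.

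**Working it through.** The plan states no sample size, effect size or variance for this contrast, so there is no figure of its own to reproduce. The check has three steps.

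**1. What the text permits.**

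| | Before conditioning (6.1) | At progression (6.2.3) |
|---|---|---|
| Source | new tissue, archival tissue, or marrow if involved | lymph node and/or marrow |
| Age of specimen | no limit | taken at the event |
| Site matched to other time point | not required | not required |
| Specimen term, offset or matching rule (8.3.4, 8.4.2) | none | none |

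**2. Size of a false ratio.** Suppose nothing truly changes. Let the main source yield mean count m and an alternative source r·m. Let f be the share of baseline specimens from the alternative source and g the share of progression specimens. The baseline mean is m(1 − f + f·r) and the progression mean is m(1 − g + g·r). A log-link model with independent covariance and time as its only covariate estimates the ratio of these means:

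false ratio = (1 − g + g·r) / (1 − f + f·r)

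The documents give none of f, g or r. All values below are assumed, with f = 0.5.

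| r | g = 0 | g = 0.25 | g = 0.5 |
|---|---|---|---|
| 0.5 | 1/0.75 = 1.33 | 0.875/0.75 = 1.17 | 0.75/0.75 = 1.00 |
| 2 | 1/1.5 = 0.67 | 1.25/1.5 = 0.83 | 1.5/1.5 = 1.00 |

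With g = 0 and f = 0.5, the ratio runs from 1.60 at r = 0.25 to 0.67 at r = 2. With g = 0 and f = 1, it runs from 4.0 to 0.50 over the same range. It is 1.00 whenever r = 1 or g = f. If g exceeds f the direction reverses: at f = 0.5, g = 0.75 and r = 0.5 it is 0.625/0.75 = 0.83. Neither size nor direction can therefore be predicted from the documents.

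**3. How many pairs there could be.** Section 8.1 gives historical PFS at 18 months of 40–50%. Expected PFS events are n × (1 − PFS):

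- 7 patients: 3.5 to 4.2
- 28 lymphoma patients: 14.0 to 16.8
- all 42 patients: 21.0 to 25.2

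At the 57% that the trial hopes for, the 28 lymphoma patients give 28 × 0.43 = 12.0. Deaths count as events, so these are upper guides to the number of pairs.

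Assume 50–80% of the 14.0–16.8 lymphoma events have a relapse biopsy, 50–80% of those match on site and preparation, and every patient has a baseline specimen. Then 14.0 × 0.5 × 0.5 = 3.5 to 16.8 × 0.8 × 0.8 = 10.8 matched pairs remain. If a baseline taken after the last line of therapy were also required, and 20–50% had one (assumed), this falls to 3.5 × 0.2 = 0.7 to 10.8 × 0.5 = 5.4.

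**The case against.** The strongest reply is that mismatch is allowed but not planned. Myeloma patients are assigned marrow biopsies at both screening and relapse, so those cohorts are largely matched on site. Baseline marrow in lymphoma is taken only where involvement is known. If the mix of sources is similar at both times, the average false ratio is near 1. All of this stands, and it is why no fixed size can be attached to the problem.

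Four stronger readings are tempting and are not supported:

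- **Group B baselines will be low-grade tissue.** Section 4.1 admits patients with "relapse with histologic transformation to diffuse large B cell lymphoma", but requires biopsy confirmation of the transformation. Tissue from the transformed disease therefore exists, and nothing says that the older block would be used instead.
- **Fixed archival counts will be set against fresh counts.** The fallback is stated for lysates and T cell DNA, not for the 8.4.2 count, and is not confined to baseline. Section 6.1 also sends samples from all disease groups for staining of fixed tissue without naming a time point, so preparation may be common to both.
- **Baselines predate treatment given years before.** No specimen ages are stated, and one route into Group B is relapse within a year of therapy.
- **1.33 or 0.67 is the expected bias.** Those values need g = 0, whereas 6.2.3 allows node or marrow at progression.

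It is also fair that this is a secondary correlative in a pilot phase, dependent on tissue being available, with no hypothesis test or decision attached. That limits the severity but does not make a pooled ratio interpretable.

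**Conclusion.** The concern holds as a minor point. Run as written, section 8.4.2 can pool non-comparable specimens and report the difference between them as change over time. It offers no means of telling the two apart. How often this would happen, and in which direction, is unknown; the ratios above are illustrations under assumed f, g and r. With at most about 14 to 17 lymphoma events at historical PFS, a few mismatched pairs could drive the estimate.

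A reader might infer that the trial's efficacy or safety conclusions are affected. They are not: the primary endpoints, sample size, expansion rule and stopping rules do not use these data, and the objective is absent from the Phase IIA list. Nor would perfect matching isolate the study drugs, since every pair also spans conditioning and transplant.

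**What to change.** - Record collection date, anatomical site and preparation for every tumour specimen.
- In 8.4.2, base the interpreted before/after contrast on within-patient pairs matched on site (node or mass versus marrow) and preparation. Report unmatched pairs separately and descriptively.
- Replace the raw absolute number with a density or proportion, or add an offset for tissue amount.
- Flag baselines taken before the last line of therapy and show results with and without them. Excluding them outright could leave almost no pairs.
- State that if too few matched pairs exist, the result will be descriptive only.
- Say whether fixed archival material can enter the 8.4.2 count.
- Reconcile the relapse-biopsy wording: 6.1 and Appendix D footnote k make it conditional, while 6.2.3 says "a confirmatory lymph node and/or bone marrow biopsy will be performed".

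The cost is SAP wording and three data fields. The analysis change needs no additional biopsy and discards no data. The downside is fewer pairs, and so less precision, in the main contrast.
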